6.6 Changes in Planned Analyses

None.

[figure not shown]
7 INDEX OF PLANNED TABLES, FIGURES, AND LISTINGS

Tables

Number	Title
14.1.1.1	Overall Disposition and Subject Accountability – FAS
14.1.1.2	Overall Disposition and Subject Accountability – PPS
14.1.1.3	Overall Disposition and Subject Accountability – SAF
14.1.2.1	Overview of Analysis Sets – Randomized Subjects
14.1.2.2	Reasons for Exclusion from Study Populations – Randomized Subjects
14.1.3	Major Protocol Deviations – FAS
14.1.4.1	Demographic and Baseline Characteristics – FAS
14.1.4.2	Demographic and Baseline Characteristics – PPS
14.1.4.3	Demographic and Baseline Characteristics – SAF
14.1.5.1	Baseline Ocular Characteristics – FAS
14.1.5.2	Baseline Ocular Characteristics – PPS
14.1.5.3	Baseline Ocular Characteristics – SAF
14.1.6.1	Study Eye Ocular Medical History – FAS
14.1.6.2	Fellow Eye Ocular Medical History – FAS
14.1.6.3	Subject Level Ocular Medical History – FAS
14.1.6.4	Non-ocular Medical History – FAS

- 14.1.7.1 Study Eye Ocular Concomitant Medications – FAS
- 14.1.7.2 Fellow Eye Ocular Concomitant Medications – FAS
- 14.1.7.3 Subject Level Ocular Concomitant Medications – FAS
- 14.1.7.4 Non-ocular Concomitant Medications – FAS
- 14.1.8 Study Medication Exposure and Compliance – SAF
- 14.2.1.1 Analyses of Change from Baseline tCFS and Dryness Score (VAS) at Day 57 – FAS
- 14.2.1.2 Analyses of Change from Baseline tCFS and Dryness Score (VAS) at Day 57 – PPS
- 14.2.2 Robustness Analyses of Change from Baseline tCFS and Dryness Score (VAS) at Day 57 (Discontinuation Rate $\geq 5\%$) – FAS
- 14.2.3 Sensitivity Analyses of Change from Baseline tCFS and Dryness Score (VAS) at Day 57 – FAS
- 14.2.4.1 Analyses of Secondary Efficacy Endpoints – FAS
- 14.2.4.2 Sensitivity Analyses of Secondary Efficacy Endpoints – FAS
- 14.2.5.1 Analysis of Dryness Score (VAS) – FAS
- 14.2.5.2 Sensitivity Analysis of Dryness Score (VAS) – FAS
- 14.2.6.1 Analysis of Study Eye tCFS – FAS
- 14.2.6.2 Analysis of Fellow Eye tCFS – FAS
- 14.2.6.3 Sensitivity Analysis of Study Eye tCFS – FAS
- 14.2.6.4 Sensitivity Analysis of Fellow Eye tCFS – FAS
- 14.2.7.1 Analysis of Study Eye Central Sub-region CFS (NEI scale) – FAS
- 14.2.7.2 Analysis of Fellow Eye Central Sub-region CFS (NEI scale) – FAS
- 14.2.7.3 Sensitivity Analysis of Study Eye Central Sub-region CFS (NEI scale) – FAS
- 14.2.7.4 Sensitivity Analysis of Fellow Eye Central Sub-region CFS (NEI scale) – FAS
- 14.2.7.5 Analysis of Study Eye Inferior Sub-region CFS (NEI scale) – FAS
- 14.2.7.6 Analysis of Fellow Eye Inferior Sub-region CFS (NEI scale) – FAS
- 14.2.7.7 Sensitivity Analysis of Study Eye Inferior Sub-region CFS (NEI scale) – FAS
- 14.2.7.8 Sensitivity Analysis of Fellow Eye Inferior Sub-region CFS (NEI scale) – FAS
- 14.2.8.1 Summary of Study Eye CFS by Sub-region (NEI scale) – FAS
- 14.2.8.2 Summary of Fellow Eye CFS by Sub-region (NEI scale) – FAS
- 14.2.9.1 Analysis of Proportion of Study Eye tCFS Responders – FAS
- 14.2.9.2 Analysis of Proportion of Fellow Eye tCFS Responders – FAS
- 14.2.9.3 Sensitivity Analysis of Proportion of Study Eye tCFS Responders – FAS
- 14.2.9.4 Sensitivity Analysis of Proportion of Fellow Eye tCFS Responders – FAS
- 14.2.10.1 Analysis of Proportion of Dryness Score Responders – FAS
- 14.2.10.2 Sensitivity Analysis of Proportion of Dryness Score Responders – FAS
- 14.2.11.1 Analysis of VAS – FAS
- 14.2.11.2 Sensitivity Analysis of VAS – FAS
- 14.2.12.1 Analysis of Ocular Surface Disease Index Score – FAS
- 14.2.12.2 Sensitivity Analysis of Ocular Surface Disease Index Score – FAS
- 14.2.13 Summary of Individual Ocular Surface Disease Index Questionnaire Items – FAS
- 14.2.14.1 Analysis of Study Eye Total Meibomian Gland Score (MGD score) – FAS
- 14.2.14.2 Analysis of Fellow Eye Total Meibomian Gland Score (MGD score) – FAS

14.2.15.1 Summary of Individual Study Eye Meibomian Gland Results – FAS
14.2.15.2 Summary of Individual Fellow Eye Meibomian Gland Results – FAS

14.3.1.1 Overview of Study Eye Ocular Adverse Events – SAF
14.3.1.2 Overview of Fellow Eye Ocular Adverse Events – SAF
14.3.1.3 Subject Level Overview of Ocular Adverse Events – SAF
14.3.1.4 Overview of Non-ocular Adverse Events – SAF
14.3.2.1 Study Eye Ocular Treatment Emergent Adverse Events by SOC – SAF
14.3.2.2 Fellow Eye Ocular Treatment Emergent Adverse Events by SOC – SAF
14.3.2.3 Non-ocular Treatment Emergent Adverse Events by SOC – SAF
14.3.3.1 Study Eye Ocular Treatment Emergent Adverse Events by SOC and PT – SAF
14.3.3.2 Fellow Eye Ocular Treatment Emergent Adverse Events by SOC and PT – SAF

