10.4.10 Safety Variables Analyses

All safety analyses will be performed on the Safety Population. The primary evaluation of safety of the active arm will be against the control arm.

Extent of Exposure

Dosing information for each treatment and each subject will be listed. Discontinuation of treatment will be summarized by treatment received. The primary reason for IMP discontinuation will also be summarized by treatment received.

Analysis of Adverse Events

Adverse events (AEs) will be coded using the MedDRA dictionary. Frequencies and percentages of subjects with TEAEs, serious TEAEs, and TEAEs causing premature discontinuation will be provided by treatment group. An AE is treatment emergent if it occurs or worsens after the first dose of trial treatment. Furthermore, frequencies will be

given of subjects with TEAEs by system organ class; by system organ class and preferred term; by system organ class, preferred term and maximal severity; by system organ class, preferred term and strongest relationship; and by system organ class, preferred term, maximal severity, and strongest relationship. Separate summaries will be performed for ocular and non-ocular AEs.

The treatment groups will be compared in regard to safety endpoints descriptively. No inferential comparison will be conducted.

Concomitant Medications

Concomitant medications will be coded using the most recent version of WHO-Drug Dictionary and summarized by treatment group.

Other safety endpoints including those assessed by visual acuity, slit-lamp biomicroscopy, dilated fundoscopy, and intraocular pressure will be summarized by treatment group and visit using descriptive statistics. Changes from baseline will also be summarized where appropriate. For assessments performed by eye, study eye and fellow eye will be summarized separately.

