6.5.9.1 Adverse Events

6.5.9.1.1 General Considerations for Analysis of Adverse Events

General considerations for AE summaries and calculations are:

- Multiple events by PT and SOC will be counted once per subject for each treatment
- For summaries by severity, the most severe event will be selected
- For summaries by relationship, the most related event will be selected

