6.5.9.1.7 Summaries of Adverse Event

Treatment-emergent AEs will be summarized. Number of subjects or eyes experiencing a TEAE will be summarized by SOC and PT by treatment group and overall. In summary tables, SOC will be presented alphabetically and events within SOC will be presented by decreasing frequency count based on the total column.

Summary tables (number and percentage of subjects) of AEs will be provided by treatment as follows:

- All treatment-emergent AEs by SOC
- All treatment-emergent AEs by SOC and PT
- All treatment-emergent AEs by SOC, PT and maximal severity
- All treatment-emergent AEs by SOC, PT and strongest relationship
- All treatment-emergent AEs by SOC, PT, maximal severity, and strongest relationship
- All serious treatment-emergent AEs by SOC and PT
- All treatment-emergent AEs leading to premature discontinuation of treatment by SOC and PT
- All non-serious treatment-emergent AEs by SOC and PT occurring at the PT level at rates of 1%, 2%, 3%, 4%, and 5% in at least one treatment arm, separately by percentage

Separate summaries will be performed for ocular and non-ocular AEs. Ocular AEs will be summarized at the subject and eye levels, with separate eye level summaries for study and fellow eye.

An overview table will be provided summarizing the number of:

- TEAEs
- Serious TEAEs
- Serious TEAEs by reason for seriousness
- TEAEs leading to premature discontinuation of treatment
- TEAEs by worst severity
- TEAEs by worst relationship
- TEAEs by pattern
- TEAEs by outcome
- TEAEs by action taken
- TEAEs by action taken related to investigational product
- TEAEs in the investigator's opinion that are ongoing and should be recorded as medical history of the NVU-004 study, and TEAEs by body system.

The treatment groups will be compared in regard to safety endpoints descriptively. No inferential comparison will be conducted.

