14.3.7.3 Non-ocular Serious Treatment Emergent Adverse Events by SOC and PT – SAF
14.3.8.1 Study Eye Ocular Treatment Emergent Adverse Events Leading to Premature Discontinuation of Treatment by SOC and PT – SAF

- 14.3.8.2 Fellow Eye Ocular Treatment Emergent Adverse Events Leading to Premature Discontinuation of Treatment by SOC and PT – SAF
- 14.3.8.3 Non-ocular Treatment Emergent Adverse Events Leading to Premature Discontinuation of Treatment by SOC and PT – SAF
- 14.3.9.1 Study Eye Ocular Non-serious Treatment Emergent Adverse Events by SOC and PT Occurring at the PT Level at Rates of 1%, 2%, 3%, 4%, and 5% in at Least one Treatment Arm – SAF
- 14.3.9.2 Fellow Eye Ocular Non-serious Treatment Emergent Adverse Events by SOC and PT Occurring at the PT Level at Rates of 1%, 2%, 3%, 4%, and 5% in at Least one Treatment Arm – SAF
- 14.3.9.3 Non-ocular Non-serious Treatment Emergent Adverse Events by SOC and PT Occurring at the PT Level at Rates of 1%, 2%, 3%, 4%, and 5% in at Least one Treatment Arm – SAF
- 14.4.1.1 Summary of Study Eye BCVA (logMAR) Results and Change from Baseline by Visit - SAF
- 14.4.1.2 Summary of Fellow Eye BCVA (logMAR) Results and Change from Baseline by Visit - SAF
- 14.4.2.1 Summary of Study Eye Slit-lamp Biomicroscopy Results by Location and Visit – SAF
- 14.4.2.2 Summary of Fellow Eye Slit-lamp Biomicroscopy Results by Location and Visit – SAF
- 14.4.3.1 Worsening Shifts in Study Eye Slit-lamp Biomicroscopy Results– SAF
- 14.4.3.2 Worsening Shifts in Fellow Eye Slit-lamp Biomicroscopy Results– SAF
- 14.4.4.1 Summary of Study Eye Dilated Fundoscopy Results by Location and Visit – SAF
- 14.4.4.2 Summary of Fellow Eye Dilated Fundoscopy Results by Location and Visit – SAF
- 14.4.5.1 Worsening Shifts in Study Eye Dilated Fundoscopy Results– SAF
- 14.4.5.2 Worsening Shifts in Fellow Eye Dilated Fundoscopy Results– SAF
- 14.4.6.1 Summary of Study Eye Intraocular Pressure and Change from Baseline by Visit – SAF
- 14.4.6.2 Summary of Fellow Eye Intraocular Pressure and Change from Baseline by Visit – SAF
- Listings
- 16.2.1 Subject Disposition
- 16.2.2.1 Inclusion Criterion
- 16.2.2.2 Exclusion Criterion
- 16.2.2.4 Protocol Deviations
- 16.2.3.1 Subjects Excluded from the Per Protocol Analysis Set
- 16.2.4.1 Demographic and Baseline Information
- 16.2.4.2 Ocular Medical History
- 16.2.4.3 Ocular Surgical History
- 16.2.4.4 Non-ocular Medical History
- 16.2.4.5 Non-ocular Surgical History
- 16.2.5.1 Dosing Compliance and Exposure

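### The SAP's table index gives ocular adverse events by preferred term only per eye, although the SAP text and protocol promise counts of subjects

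*SAP*

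**What the plan says.** **Protocol 10.4.10.** After the overall counts, frequencies are to be "given of subjects with TEAEs by system organ class; by system organ class and preferred term", and then by severity and relationship. Ocular and non-ocular events are to be summarized separately. The synopsis says the same.

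**SAP 6.5.9.1.1.** The counting rule is per subject: "Multiple events by PT and SOC will be counted once per subject for each treatment".

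**SAP 6.5.9.1.7.** The list of breakdowns opens with "Summary tables (number and percentage of subjects) of AEs will be provided by treatment as follows". For ocular events it adds: "Ocular AEs will be summarized at the subject and eye levels, with separate eye level summaries for study and fellow eye". A looser sentence in the same section reads "Number of subjects or eyes experiencing a TEAE will be summarized by SOC and PT by treatment group and overall".

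**SAP section 7.** Each family from 14.3.2 to 14.3.9 has three tables: .1 study eye, .2 fellow eye, .3 non-ocular. Examples are "Study Eye Ocular Treatment Emergent Adverse Events by SOC and PT" and "Fellow Eye Ocular Treatment Emergent Adverse Events Leading to Premature Discontinuation of Treatment by SOC and PT". Only the overview family 14.3.1 has a fourth, subject-level ocular table (14.3.1.3). The finest breakdown in the overview contents listed in 6.5.9.1.7 is body system.

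**SAP 6.6** declares no change from the planned analyses.

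**The concern.** Ocular and non-ocular adverse events are the first-listed safety endpoint. Both eyes are dosed. The study eye is picked by eligibility and the higher staining score at Visit 1, with the right eye taken in a tie (SAP 6.5.7.2), so the study/fellow split is an efficacy device with no particular safety meaning. The usual safety question is how many people in each arm had a given event. For any named ocular event, no planned table answers it.

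Two outputs are affected most. The 14.3.9 tables select terms by rate cut-offs from 1% to 5%, and for ocular events those cut-offs would be applied to eyes. The 14.3.8 tables cover events that led to stopping treatment. Stopping is something a subject does, yet a subject who stops for an event in both eyes appears in both ocular tables.

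**Working it through.** There is no stated figure to reproduce, so the check sets the index against the text and then asks whether the promised number can be recovered.

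**1. Count the tables (SAP section 7).** The eight families are: organ class (14.3.2), preferred term (14.3.3), severity (14.3.4), relationship (14.3.5), severity with relationship (14.3.6), serious (14.3.7), discontinuation (14.3.8) and non-serious by rate cut-off (14.3.9).

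- Tables in total: 8 × 3 = 24.
- Ocular, per eye: 8 × 2 = 16, of which 7 × 2 = 14 are by preferred term.
- Non-ocular: 8.
- Ocular, per subject: 0.

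**2. Could redaction explain it?** In 14.3.1 the subject-level ocular table takes .3 and the non-ocular table .4. In the other eight families the non-ocular table takes .3 directly after the fellow eye. A hidden subject-level table would have to be a .4 in all eight families, out of the order used in 14.3.1.

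**3. Compare similar data.** SAP 6.5.4.2 and 6.5.4.3 make the same subject-and-eye promise for ocular medical history and ophthalmic concomitant medications. Both have a subject-level table in the index (14.1.6.3 and 14.1.7.3). Adverse events by organ class or preferred term do not.

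**4. Can the subject count be derived from the two eye tables?** For one preferred term in one arm, let a be the study-eye count, b the fellow-eye count and c the number of subjects affected in both eyes. Then

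subjects = a + b − c, with c between 0 and min(a, b),

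so the subject count lies between max(a, b) and a + b. No planned table gives c.

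**5. Size.** Take 280 subjects per arm (SAP 6.1), hence 280 study eyes and 280 fellow eyes. The eye counts below are assumptions; the documents give none.

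| Study eyes | Fellow eyes | Rate in each eye table | Subjects, all bilateral | Subjects, all unilateral |
|---|---|---|---|---|
| 2 | 2 | 2/280 = 0.7% | 2 (0.7%) | 4 (1.4%) |
| 3 | 3 | 3/280 = 1.1% | 3 (1.1%) | 6 (2.1%) |
| 8 | 8 | 8/280 = 2.9% | 8 (2.9%) | 16 (5.7%) |

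**6. Effect on the cut-offs.** One percent of 280 is 2.8, so a term needs 3 eyes, or 3 subjects, to reach 1%. With 2 and 2 it misses the cut-off in both eye tables. At subject level it reaches 1% whenever at most one subject is bilateral: 2 + 2 − 1 = 3, and 3/280 = 1.1%. With equal denominators the error runs one way. Because the subject count is never below max(a, b), the eye tables can drop a term that a subject-level table would show, but not the reverse.

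**The case against.** The strongest reply is that the analysis is already prescribed and only a list of titles lags behind. The text asks for counts of subjects, fixes the once-per-subject rule and names the subject level for ocular events. The index is not flawless elsewhere either: its listing numbers pass from 16.2.2.2 to 16.2.2.4. That much stands. This is an inconsistency between text and index, and a reader should not infer that the sponsor weighed subject-level analysis and rejected it. It still needs settling, because the index is the list of outputs to be produced.

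Three stronger readings are tempting, and the documents do not support them.

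- *Subject-level ocular safety is missing altogether.* It is not. Protocol 10.4.10 first asks for overall counts ("Frequencies and percentages of subjects with TEAEs, serious TEAEs, and TEAEs causing premature discontinuation will be provided by treatment group"). For ocular events these are covered by 14.3.1.3, since the overview contents in SAP 6.5.9.1.7 include serious events, events leading to discontinuation, worst severity and worst relationship. Its body-system line may also cover part of what a subject-level 14.3.2 would show. For the same reason the phase 2 ocular incidence of 4.5% to 11.7% (protocol 2.4) cannot size the gap: it is an overall rate, and the overview would report the matching figure correctly.
- *The eye tables understate event rates.* A correctly labelled eye table gives the right rate for that eye. It does not give a different quantity, the share of subjects.
- *Ocular and non-ocular events must be combined in one table.* Both documents specify separate summaries, so a combined table is optional.

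It can also be said that subject counts per term could be assembled from listing 16.2.7.1 or the analysis datasets. They could, but a listing is not the table of frequencies by arm that the protocol promises.

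**Conclusion.** The point holds at the level of organ class and preferred term, including the severity, relationship, serious, discontinuation and rate cut-off breakdowns. In the eight detailed families the index plans 16 per-eye ocular tables and no per-subject ones, against SAP 6.5.9.1.1, SAP 6.5.9.1.7 and protocol 10.4.10. The phrase allowing subjects or eyes in 6.5.9.1.7 is loose, but the explicit sentence on both levels and the protocol settle what was meant.

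How far the eye tables differ from subject incidence depends on how often events affect both eyes, which the documents do not say. If every event is bilateral there is no difference; if every event is unilateral and evenly split between eyes, the subject rate is twice the rate in each eye table. The practical harm is that a named ocular event has no tabulated per-subject incidence and that a less common term can slip under the 14.3.9 cut-offs. Efficacy, type I error and trial conduct are untouched, and the safety comparison is descriptive throughout. The gap is worth closing because the outputs concerned are core safety tables and the remedy is cheap.

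**What to change.** Amend SAP section 7, before database lock and unmasking, as SAP section 4 allows:

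1. Add one subject-level ocular table to each family 14.3.2 to 14.3.9 (event in either eye, each subject counted once per term), following the four-table layout of 14.3.1. The eight families then hold 8 × 4 = 32 tables.
2. State in 6.5.9.1.7 that the ocular rate cut-offs in 14.3.9 apply to subject counts.
3. Keep the study-eye and fellow-eye tables as supportive.

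A combined ocular and non-ocular table may be added if wanted, but the documents do not call for it. The cost is about eight table shells built from existing datasets, with no new data collection.

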14.3.3.3 Non-ocular Treatment Emergent Adverse Events by SOC and PT – SAF
14.3.4.1 Study Eye Ocular Treatment Emergent Adverse Events by SOC, PT, and Maximal Severity – SAF
14.3.4.2 Fellow Eye Ocular Treatment Emergent Adverse Events by SOC, PT, and Maximal Severity – SAF
14.3.4.3 Non-ocular Treatment Emergent Adverse Events by SOC, PT, and Maximal Severity – SAF
14.3.5.1 Study Eye Ocular Treatment Emergent Adverse Events by SOC, PT, and Strongest Relationship – SAF
14.3.5.2 Fellow Eye Ocular Treatment Emergent Adverse Events by SOC, PT, and Strongest Relationship – SAF
14.3.5.3 Non-ocular Treatment Emergent Adverse Events by SOC, PT, and Strongest Relationship – SAF
14.3.6.1 Study Eye Ocular Treatment Emergent Adverse Events by SOC, PT, Maximal Severity, and Strongest Relationship – SAF
14.3.6.2 Fellow Eye Ocular Treatment Emergent Adverse Events by SOC, PT, Maximal Severity, and Strongest Relationship – SAF
14.3.6.3 Non-ocular Treatment Emergent Adverse Events by SOC, PT, Maximal Severity, and Strongest Relationship – SAF
14.3.7.1 Study Eye Ocular Serious Treatment Emergent Adverse Events by SOC and PT – SAF
14.3.7.2 Fellow Eye Ocular Serious Treatment Emergent Adverse Events by SOC and PT – SAF
14.3.7.3 Non-ocular Serious Treatment Emergent Adverse Events by SOC and PT – SAF
14.3.8.1 Study Eye Ocular Treatment Emergent Adverse Events Leading to Premature Discontinuation of Treatment by SOC and PT – SAF

- 14.3.8.2 Fellow Eye Ocular Treatment Emergent Adverse Events Leading to Premature Discontinuation of Treatment by SOC and PT – SAF
- 14.3.8.3 Non-ocular Treatment Emergent Adverse Events Leading to Premature Discontinuation of Treatment by SOC and PT – SAF
- 14.3.9.1 Study Eye Ocular Non-serious Treatment Emergent Adverse Events by SOC and PT Occurring at the PT Level at Rates of 1%, 2%, 3%, 4%, and 5% in at Least one Treatment Arm – SAF
- 14.3.9.2 Fellow Eye Ocular Non-serious Treatment Emergent Adverse Events by SOC and PT Occurring at the PT Level at Rates of 1%, 2%, 3%, 4%, and 5% in at Least one Treatment Arm – SAF
- 14.3.9.3 Non-ocular Non-serious Treatment Emergent Adverse Events by SOC and PT Occurring at the PT Level at Rates of 1%, 2%, 3%, 4%, and 5% in at Least one Treatment Arm – SAF
- 14.4.1.1 Summary of Study Eye BCVA (logMAR) Results and Change from Baseline by Visit - SAF
- 14.4.1.2 Summary of Fellow Eye BCVA (logMAR) Results and Change from Baseline by Visit - SAF
- 14.4.2.1 Summary of Study Eye Slit-lamp Biomicroscopy Results by Location and Visit – SAF
- 14.4.2.2 Summary of Fellow Eye Slit-lamp Biomicroscopy Results by Location and Visit – SAF
- 14.4.3.1 Worsening Shifts in Study Eye Slit-lamp Biomicroscopy Results– SAF
- 14.4.3.2 Worsening Shifts in Fellow Eye Slit-lamp Biomicroscopy Results– SAF
- 14.4.4.1 Summary of Study Eye Dilated Fundoscopy Results by Location and Visit – SAF
- 14.4.4.2 Summary of Fellow Eye Dilated Fundoscopy Results by Location and Visit – SAF
- 14.4.5.1 Worsening Shifts in Study Eye Dilated Fundoscopy Results– SAF
- 14.4.5.2 Worsening Shifts in Fellow Eye Dilated Fundoscopy Results– SAF
- 14.4.6.1 Summary of Study Eye Intraocular Pressure and Change from Baseline by Visit – SAF
- 14.4.6.2 Summary of Fellow Eye Intraocular Pressure and Change from Baseline by Visit – SAF
- Listings
- 16.2.1 Subject Disposition
- 16.2.2.1 Inclusion Criterion
- 16.2.2.2 Exclusion Criterion
- 16.2.2.4 Protocol Deviations
- 16.2.3.1 Subjects Excluded from the Per Protocol Analysis Set
- 16.2.4.1 Demographic and Baseline Information
- 16.2.4.2 Ocular Medical History
- 16.2.4.3 Ocular Surgical History
- 16.2.4.4 Non-ocular Medical History
- 16.2.4.5 Non-ocular Surgical History
- 16.2.5.1 Dosing Compliance and Exposure

- 16.2.5.2 Dispense Investigational Drug
- 16.2.5.3 Daily Dosing Diary
- 16.2.5.4 Randomized and Actual Treatments
- 16.2.6.1 Corneal Fluorescein Staining (CFS) by Area and Total Score
- 16.2.6.2 Dryness Score (VAS)
- 16.2.6.3 Ocular Symptoms (VAS)
- 16.2.6.4 Ocular Surface Disease Index (OSDI)
- 16.2.6.5 Meibomian Gland Assessment (MGD Score)
- 16.2.6.6 Schirmer's Test I (Without Anesthesia)
- 16.2.6.7 Tear Film Break-up Time (TFBUT)
- 16.2.6.8 Instillation Comfort Questionnaire
- 16.2.6.9 Eyedrop Acceptability Questionnaire
- 16.2.6.10 Collection of Returned Investigational Product
- 16.2.7.1 All Adverse Events by SOC, PT, and Verbatim Term
- 16.2.7.2 Adverse Events Leading to Premature Discontinuation of Treatment
- 16.2.7.3 Serious Adverse Events
- 16.2.7.4 Subject Deaths
- 16.2.8.1 Pregnancy Test
- 16.2.9.1 Visual Acuity
- 16.2.9.2 Slit-lamp Biomicroscopy
- 16.2.9.3 Dilated Fundoscopy
- 16.2.9.4 Intraocular Pressure
- 16.2.9.5 Ocular Concomitant Medications
- 16.2.9.6 Ocular Concomitant Therapies
- 16.2.9.7 Non-ocular Concomitant Medications
- 16.2.9.8 Non-ocular Concomitant Therapies
- 16.3.1 Unscheduled Visits
- 16.3.2 Subject Completion

